3.1.4 Treatment

3.1.4.1 Study Treatment Duration (MSI-H Cohorts Only)

In MSI-H Cohorts only [mStage 1/2, cStage 1/2, C3 (1L), C5 (BMS-986016 /anti-LAG3] study treatment will be given until one of the following conditions is met, whichever occurs first:

- 1) Disease progression, except for subjects eligible for treatment beyond progression (See Section 4.3.8)
- 2) Unacceptable toxicity
- 3) Withdrawal of consent
- 4) Maximum clinical benefit (optional) Subjects who attain all of the following criteria will have the option to discontinue treatment:
 - a) Maximum clinical benefit per Investigator
 - b) Minimum 12 months of treatment (in the absence of unacceptable toxicity) after date of first response (PR or CR) if the patient achieved response
 - c) Minimum 24 months between first dose of study treatment and discontinuation for maximum clinical benefit
 - d) No progression since week 12 of study treatment.

Restaging imaging must be evaluated before decision to discontinue at maximum clinical benefit. If the subject's BOR is SD, it is encouraged to ensure approximately 24 months of treatment before the decision to discontinue at maximum clinical benefit in order to capture any late responses.

Please see Section 3.1.4.8 and Figure 3.1.4.8-1: for treatment options upon progression for subjects who discontinue at maximum clinical benefit per above description. All criteria

listed above must have been met and the subject must have continued required safety and efficacy follow up procedures to be eligible for re-initiation consideration.

Re-initiation of treatment is an option for eligible MSI-H subjects who progress within 1 year (≤ 52 weeks) of discontinuation for maximum clinical benefit. Subjects who discontinuation for maximum clinical benefit and progress after 52 weeks of follow-up will not have the option to re-initiate treatment.

5) The end of study

3.1.4.2 MSI-H Nivolumab Monotherapy (Arm N): mStage 1 and 2

- Administration of nivolumab should begin within 3 days of treatment assignment.
- Women of child bearing potential (WOCBP) must have a negative pregnancy test to be done within 24 hours prior to first dose, and then every 4 weeks (± 1 week) regardless of dosing schedule.
- On trial laboratory and vital sign assessments (after D1W1) should be drawn within 72 hours prior to dosing according to the schedule in Table 5.1-2. Specific laboratories will be performed more frequently during the first dose administration (according to Table 5.1-2).
- Adverse event assessments should be documented at each clinic visit.

Biomarker, PK, and immunogenicity samples will be obtained according to the schedules in Table 5.5.1-2 and Table 5.6.8-1.

- Study drug dosing may be delayed for toxicity up to 6 weeks from the last dose. See Section 4.3.3.
- Patient-reported outcome(s) (PRO) instruments (EORTC QLQ-C30 & EQ-5D Questionnaires) will be completed for subjects, except for those enrolled in the non-MSI-H Safety Cohort, following drug vial assignment but before first dose and every 6 weeks thereafter per Table 5.1-2.
- Nivolumab is administered as an IV infusion at a dose of 480 mg Q4W (replacing the dose of 3 mg/kg every 2 weeks) until discontinuation of study therapy and for reasons described in Section 3.1.4.1, Study Treatment Discontinuation. in subjects receiving nivolumab beyond progression, discontinuation due to toxicity, withdrawal of consent, or the study ends.
- This phase ends when the subject is discontinued from study therapy for reasons specified in Section 3.5 and Section 4.3.6. Subjects who discontinue treatment at Maximum Clinical Benefit as specified in Section 3.1.4.1 may re-initiate treatment (see Sections 3.1.4.8 and 4.3.1) if all eligibility criteria are met (Section 4.3.9). All subjects will proceed to follow-up as described in Section 3.1.9 and in Table 5.1-7 regardless of the reason for discontinuation from the original treatment phase of the study. Study schedule of assessments for re-initiation screening, re-initiation treatment, and follow-up after re-initiation are presented in Section 5.1.

3.1.4.3 MSI-H Nivolumab + Ipilimumab (Arm N+I): cStage 1 and 2

 Administration of nivolumab in combination with ipilimumab should begin within 3 days from treatment assignment

• Women of child bearing potential (WOCBP) must have a negative pregnancy test within 24 hours prior to first dose, and then every 4 weeks (1 week) regardless of dosing schedule.

- Adverse event assessments will be documented at each visit throughout the study.
- On trial laboratory and vital sign assessments (after D1W1) should be drawn within 72 hours prior to dosing according to the schedule in Table 5.1-3. Specific laboratories will be performed more frequently during the treatment administration (according to Table 5.1-3).

Biomarker, PK and immunogenicity samples will be obtained according to the schedules in Table 5.5.1-1 and Table 5.6.8-2.

- Study drug dosing may be delayed for toxicity up to 6 weeks from the last dose. See Section 4.3.3.
- Patient-reported outcome(s) (PRO) instruments (EORTC QLQ-C30 & EQ-5D Questionnaires) will be completed for all subjects, except for those enrolled in the non-MSI-H Safety Cohort, following drug vial assignment but before first dose, and every 6 weeks thereafter per Table 5.1-3.
- For Weeks 1-12, the non-MSI-H safety cohort will provide the dosing level for the every three week dosing of nivolumab in combination with ipilimumab:
- For Weeks 13 and following (beyond Dose 4 of nivolumab in combination with ipilimumab), nivolumab is administered as an IV infusion at a dose of 480 mg Q4W (replacing the dose of 3 mg/kg every 2 weeks).
- Administration of nivolumab in combination with ipilimumab (Dose 1 through Dose 4 of combination) or nivolumab alone (beyond Dose 4/Week 12 of combination) continues until discontinuation of study therapy for reasons described in Section 3.1.4.1, "Study Treatment Duration".
- This phase ends when the subject is discontinued from study therapy for reasons specified in Section 3.5 and Section 4.3.6. Subjects who discontinue treatment at Maximum Clinical Benefit as specified in Section 3.1.4.1 may re-initiate treatment (see Sections 3.1.4.8 and 4.3.1) if all eligibility criteria are met (Section 4.3.9.). All subjects will proceed to follow-up as described in Section 3.1.9 and in Table 5.1-7 regardless of the reason for discontinuation from the original treatment phase of the study. Study schedule of assessments for re-initiation screening, re-initiation treatment, and follow-up after re-initiation are presented in Section 5.1.

3.1.4.4 Non-MSI-H Safety Cohort (Nivolumab + Ipilimumab)

- Administration of nivolumab in combination with ipilimumab should begin within 3 days of treatment assignment.
- Women of child bearing potential (WOCBP) must have a negative pregnancy test within 24 hours prior to first dose, and then every 4 weeks (±1 week) regardless of dosing schedule.
- Dose Escalation Phase:
 - Dose Level -1, Nivolumab 0.3 mg/kg IV combined with ipilimumab 1 mg/kg IV Q3W for 4 doses, then nivolumab 3 mg/kg IV Q2W
 - Dose Level 1, Nivolumab 1 mg/kg IV combined with ipilimumab 1 mg/kg IV Q3W for 4 doses, then nivolumab 3 mg/kg IV Q2W.

- Dose Level 2: Randomization (1:1) to the following arms
 - ◆ **Dose Level 2a:** Nivolumab 1 mg/kg IV combined with ipilimumab 3 mg/kg IV Q3W for 4 doses, then nivolumab 3 mg/kg IV Q2W.
 - ◆ **Dose Level 2b:** Nivolumab 3 mg/kg IV combined with ipilimumab 1 mg/kg IV Q3W for 4 doses, then nivolumab 3 mg/kg IV Q2W.

Staged Enrollment Phase: Dose Level determined in Dose Escalation Phase. See Table 3.1.2.1-1, Table 3.1.2.1-2, Table 3.1.2.1-3, and Table 3.1.2.1-4.

- Adverse event assessments will be documented at each visit throughout the study.
- On-study laboratory assessments (after D1W1) should be drawn within 72 hours prior to dosing according to the schedule in Table 5.1-3.

Biomarker, PK, and immunogenicity samples will be obtained according to the schedules in Table 5.5.1-1 and Table 5.6.8-2.

- Study drug dosing may be delayed for toxicity for up to 6 weeks from the last dose. See Section 4.3.3.
- For Weeks 13 and following (beyond Dose 4 of nivolumab in combination with ipilimumab), nivolumab is administered as an IV infusion at a dose of 3 mg/kg every 2 weeks.
- Administration of nivolumab in combination with ipilimumab (Dose 1 through Dose 4 of combination) or nivolumab alone (beyond Dose 4/Week 12 of combination) continues until disease progression or until discontinuation of study therapy in subjects receiving study therapy beyond progression, discontinuation due to toxicity, withdrawal of consent, or the study ends.
- This phase ends when the subject is discontinued from study therapy. Please refer to Section 3.5 and Section 4.3.6 for reasons for discontinuation.

3.1.4.5 MSI-H C3 Cohort (No Prior Treatment in Metastatic Setting, Nivolumab + Ipilimumab)

- Administration of nivolumab in combination with ipilimumab should begin within 3 days of treatment assignment.
- Women of child bearing potential (WOCBP) must have a negative pregnancy test within 24 hours prior to first dose, and then every 4 weeks (±1 week) regardless of dosing schedule.
- Adverse event assessments will be documented at each visit throughout the study.
- On-study laboratory assessments (after D1W1) should be drawn within 72 hours prior to dosing according to the schedule in Table 5.1-4.
- Biomarker, PK and immunogenicity samples will be obtained according to the schedules in Table 5.5.1-3 and Table 5.6.8-3.
- Study drug dosing may be delayed for toxicity for up to 6 weeks from the last dose. See Section 4.3.3.

• Administration of study drug continues until discontinuation of study therapy for reasons described in Section 3.1.4.1, "Study Treatment Duration".

- Patient-reported outcome(s) (PRO) instruments (EORTC QLQ-C30 & EQ-5D Questionnaires) will be completed following drug vial assignment but before first dose, and every 6 weeks thereafter per Section 5.7.
- This phase ends when the subject is discontinued from study therapy for reasons specified in Section 3.5 and Section 4.3.6. Subjects who discontinue treatment at Maximum Clinical Benefit as specified in Section 3.1.4.1 may re-initiate treatment (see Sections 3.1.4.8 and 4.3.1) if all eligibility criteria are met (Section 4.3.9.). All subjects will proceed to follow-up as described in Section 3.1.9 and in Table 5.1-7 regardless of the reason for discontinuation from the original treatment phase of the study. Study schedule of assessments for re-initiation screening, re-initiation treatment, and follow-up after re-initiation are presented in Section 5.1.

3.1.4.6 MSI-H C5 Cohort (2L in Metastatic Setting, Nivolumab + BMS-986016)

- Administration of nivolumab in combination with BMS-986016 should begin within 3 days of treatment assignment.
- Women of child bearing potential (WOCBP) must have a negative pregnancy test within 24 hours prior to first dose, and then every 4 weeks (±1 week) regardless of dosing schedule.
- Adverse event assessments will be documented at each visit throughout the study.
- Neurological exams by a neurologist should be performed in subjects who experience a study drug related ≥ Grade 2 neurological AE.
- On-study laboratory assessments, including cardiac troponin levels, (after D1W1) should be drawn within 72 hours prior to dosing according to the schedule in Table 5.1-5.
- 12-lead ECG to be performed within 72 hours prior to dosing
- Biomarker, PK, and immunogenicity samples will be obtained according to the schedules in Table 5.5.1-4 and Table 5.6.8-3.
- Study drug dosing may be delayed for toxicity for up to 6 weeks from the last dose. See Section 4.3.3.
- Administration of study drug continues until discontinuation of study therapy for reasons described in Section 3.1.4.1, "Study Treatment Duration"...
- Patient-reported outcome(s) (PRO) instruments (EORTC QLQ-C30 & EQ-5D Questionnaires) will be completed following drug vial assignment but before first dose, and every 6 weeks thereafter per Table 5.1-5.
- This phase ends when the subject is discontinued from study therapy for reasons specified in Section 3.5 and Section 4.3.6. Subjects who discontinue treatment at Maximum Clinical Benefit as specified in Section 3.1.4.1 may re-initiate treatment (see Sections 3.1.4.8 and 4.3.1) if all eligibility criteria are met (Section 4.3.9.). All subjects will proceed to follow-up as described in Section 3.1.9 and in Table 5.1-7 regardless of the reason for discontinuation from the original treatment phase of the study. Study schedule of assessments for re-initiation screening, re-initiation treatment, and follow-up after re-initiation are presented in Section 5.1.

3.1.4.7 non-MSI-H C6 Cohort (Nivolumab + Daratumumab)

- Administration of study drug should begin within 3 days of treatment assignment.
- Women of child bearing potential (WOCBP) must have a negative pregnancy test within 24 hours prior to first dose, and then every 4 weeks (±1 week) regardless of dosing schedule.
- Adverse event assessments will be documented at each visit throughout the study.
- On-study laboratory assessments (after D1W1) should be drawn within 72 hours prior to dosing according to the schedule in Table 5.1-6.
- Herpes Zoster virus antiviral prophylaxis should be initiated within 1 week after starting daratumumab and continue during the Treatment Phase per institutional guidelines, and for 3 months following treatment discontinuation.
- Biomarker, PK, and immunogenicity samples will be obtained according to the schedules in Table 5.5.1-5 and Table 5.6.8-3.
- Study drug dosing may be delayed for toxicity for up to 6 weeks from the last dose. See Section 4.3.3.
- Administration of study drug continues until disease progression or until discontinuation of study therapy in subjects receiving study therapy beyond progression, discontinuation due to toxicity, withdrawal of consent, or the study ends.
- Patient-reported outcome(s) (PRO) instruments (EORTC QLQ-C30 & EQ-5D Questionnaires) will be completed following drug vial assignment but before first dose, and every 6 weeks through Week 24 and then at each dose, starting with Week 25 according to Table 5.1-6.
- This phase ends when the subject is discontinued from study therapy. Please refer to Section 3.5 and Section 4.3.6 for reasons for discontinuation.

3.1.4.8 Treatment Options Upon Progression after Treatment Discontinuation At Maximum Clinical Benefit

Subjects who have discontinued study treatment after achieving maximum clinical benefit as specified in Section 3.1.4.1 must continue imaging every 12 weeks, and the investigator must ensure close monitoring of symptoms and complete safety follow up as indicated for AEs.

• If progression occurs ≤ 52 weeks after last dose of study treatment, subjects have the option to re-initiate treatment with nivolumab monotherapy, or the combination of nivolumab with ipilimumab or with BMS-986016 (anti-LAG3) based on the initial cohort assignment, following new baseline assessments for eligibility.

The inclusion/exclusion criteria for re-initiation are described in Section 4.3.9. Re-initiation treatment schedules are described in Section 4.3.1 and Table 4.3.1-1. Time and events schedule of study assessments during re-initiation screening, during re-initiation treatment and during follow-up after re-initiation are included in Section 5.1

Treatment duration after re-initiation, inclusive of treatment beyond progression, will be for a maximum of 24 months.

[figure not shown]
• If progression occurs > 52 weeks after last dose of study treatment, continue survival follow-up per Table 5.1-7.

Re-initiation of treatment is not permitted after 52 weeks of discontinuation at maximum clinical benefit.

Subjects who discontinue re-initiated treatment for PD are eligible for treatment beyond progression (See Section 4.3.8).

Treatment options for subjects in MSI-H cohorts who discontinue treatment at maximum clinical benefit are presented below:

Figure 3.1.4.8-1: Treatment Options at Progression for MSI-H subjects who Discontinue Treatment at Maximum Clinical Benefit

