3.1.9 Follow up

3.1.9.1 Follow -up for all Cohorts After Initial Study Treatment

Follow-up begins when the decision to discontinue a subject from study therapy is made (no further treatment with study therapy).

Subjects who started a systemic cancer treatment outside of this study will not continue with tumor imaging assessments.

Subjects who discontinue treatment for reasons other than tumor progression will continue to have tumor imaging assessments beginning 6 weeks (\pm 1 week) after first dose and continuing every 6 weeks (\pm 1 week) for the first 24 weeks from first dose, and every 12 weeks (\pm 1 week) thereafter until disease progression (investigator-assessed RECIST 1.1-defined progression).

In order to help reduce unnecessary participant burden and help optimize participant safety by reducing the possible radiation exposure risk of a secondary malignancy, investigators should reduce scan frequency for participants having disease control 3 years after the first dose per Table 5.1-14b. The participant's tumor assessment schedule should be modified to every 24 weeks, unless clinically indicated, to continue tumor assessments every 12 weeks.

- Subjects will be followed for drug-related toxicities until these toxicities resolve, return to baseline, or are deemed irreversible. All adverse events will be documented for a minimum of 100 days after last dose.
- After completion of the first two follow-up visits, subjects enrolled in the MSI-H cohort (Cohorts N and N+I) and Cohorts C3, C4, C5, and C6 will continue to survival follow-up per Table 5.1-7. Please see Section 3.1.10 for end of the study definition and duration of follow-up for survival.
- Refer to Table 5.1-7 for additional follow-up assessments.

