Table 5.1-6: Short-term Procedural Outline for C6 Cohort [Nivolumab + Daratumumab] non-MSI-H

Procedure	To Be Performed at Each Dosing Visit, Unless Otherwise Specified in Notes or Separate Table	Notes Visit Window : ± 2 Days
		The dosing calculations should be based on the body weight. All doses should be rounded to the nearest milligram.

Procedure	Follow Up, Visits 1 and 2 ^a	Survival Follow-Up Visits ^b	Notes
Safety Assessments			
Targeted Physical Examination	X		To assess for potential late emergent study drug related issues
			Targeted examination must include at a minimum the following body systems:
			Cardiovascular
			Gastrointestinal
			Pulmonary
			Neurological exam for subjects with brain metastases
Adverse Events Assessment	X		In Survival Follow-Up period only to include toxicities from study therapy
ECG	X		Only at FU1
Review of Concomitant Medication	X	X	Subsequent Cancer Therapy
Laboratory Tests	Х		CBC w/ differential and platelet count, LFTs, BUN or serum urea level, creatinine, Ca, Mg, Na, K, Cl, LDH, Glucose, amylase, lipase, TSH (+ reflex Free T4 and Free T3)
			To be done at FU1. To be repeated at FU2 if study related toxicity persists.
Troponin	X	X*	Performed for the C5 Cohort Only. All results should be checked as soon as possible.
			*Troponin testing as clinically indicated, at the discretion of the treating physician during survival follow-up.
Pregnancy Test (WOCBP only)	X		Serum or urine
Efficacy Assessments			
Tumor Imaging Assessment	See note	See note	Refer to Figure 3.1.4.8-1.
rumor imaging Assessment	See note	See note	See separate Table 5.1-14

Table 5.1-7: Follow-Up Period (All treatment groups, CA209142)			
Procedure	Follow Up, Visits 1 and 2 ^a	Survival Follow-Up Visits ^b	Notes
Outcomes Research Assessment			
EORTC QLQ-C30 & EQ-5D Questionnaires	X	X*	For all subjects except subjects in independent non-MSI safety cohort. *Only EQ-5D Questionnaire is required at Survival Follow-Up Visits
Herpes Zoster Virus Antiviral Prophylaxis	X		See Section 3.4.2.3 Initiate antiviral prophylaxis within 1 week after starting daratumumab. Continue antiviral prophylaxis during the Treatment Phase as per institutional guidelines, and for 3 months following treatment discontinuation.
Subject Status			

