Survival Status		X	Every 3 months after F-U 2 (R); may be accomplished by visit, phone contact or email, to assess subsequent anti-cancer therapy for a minimum of 5 years, in all cohorts. (Please see Section 3.1.10 for end of the study definition.)		

Subjects must be followed for at least 100 days after last dose of study therapy. Follow-up visit #1 after re-initiation (FU1 R) occurs approximately 35 days (± 7 days) after last dose or coinciding with the date of discontinuation (± 7 days) if date of discontinuation is greater than 35 days after last dose. Follow up after re-initiation visit #2 (FU2 R) occurs approximately 80 days (± 7 days) after FU1 (R).

Table 5.1-14a: Standard Tumor Imaging Assessment

Tumor imaging assessments will occur every 6 weeks from the date of first dose (\pm 1 week) for the first 24 weeks, then every 12 weeks (\pm 1 week) thereafter until disease progression or treatment is discontinued (whichever occurs later).

Table 5.1-14b: Reduced Tumor Imaging Assessment

All Subjects (Except Re-initiation Subjects)	Re-initiation Subjects
Scans every 12 weeks (\pm 1 week) for 3 years after first dose, then every 24 weeks (\pm 2 weeks) thereafter*	Scans every 12 weeks (\pm 1 week) for 3 years after first dose following reinitiation, then every 24 weeks (\pm 2 weeks) thereafter ^a

 $^{^{\}mathrm{a}}$ Scans may continue every 12 weeks (\pm 1 week) if clinically indicated.

Notes: CT or MRI chest, abdomen, pelvis and all known sites of disease. Use same imaging method as was used at screening/baseline.

Subjects with a history of brain metastasis may have surveillance MRI approximately every 12 weeks from the date of first dose, or sooner if clinically indicated.

Protocol Amendment No: 09

b Survival visits = every 3 months from FU2 (R). Survival visits will be conducted for all MSI-H subjects who have re-initiated treatment.

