5.4 Efficacy Assessments

• Study evaluations will take place in accordance with the flow charts in Section 5.1. Baseline assessments should be performed within 28 days prior to the first dose utilizing CT or MRI. In addition to chest, abdomen, and pelvis, all known sites of disease should be assessed at baseline. Subsequent assessments should include chest, abdomen, and pelvis, and all known sites of disease and should use the same imaging method as was used at baseline. Baseline MRI for brain should be done for known or suspected disease. Subjects with a history of brain metastasis should have surveillance MRI approximately every 12 weeks, or sooner if clinically indicated. Subjects will be evaluated for tumor response beginning 6 weeks (±1 week) from first dose and continuing every 6 weeks (±1 week) for the first 24 weeks and every 12 weeks (±1 week) thereafter, until disease progression is documented or treatment is discontinued (whichever occurs later). Tumor imaging assessments for ongoing study treatment decisions will be completed by the investigator using RECIST (Response Evaluation Criteria in Solid Tumors) 1.1 criteria, Appendix 3. Confirmation of PR and/or CR is required after at least 4 weeks from the initial scan reporting response. Confirmation of progression is not required.

For re-initiated subjects, assessments will only be performed locally and the imaging vendor will collect scans. During Re-initiation, tumor imaging assessments should occur every 6 weeks from

the date of re-initiation of treatment (± 1 week) for the first 24 weeks, then every 12 weeks (± 1 week) thereafter until disease progression or treatment is discontinued (whichever occurs later).

In order to help reduce unnecessary participant burden and help optimize participant safety by reducing the possible radiation exposure risk of a secondary malignancy, investigators should reduce scan frequency for participants having disease control at 3 years, per Table 5.1-14b. 3 years after the first dose or 3 years after re-initiation dose, as the case may be, the participant's tumor assessment schedule should be modified to every 24 weeks unless clinically indicated to continue tumor assessments every 12 weeks.

Immune-related response criteria using unidimensional measurements may be used to describe tumor shrinkage following disease progression. This phenomenon has been described for ipilimumab as well as for nivolumab.

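### The reduced 24-weekly scan schedule does not exempt subjects still in the 52-week re-initiation window, and the protocol words that window's start and closing event inconsistently (minor)

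*Combined protocol and SAP*

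**What the plan says.** **Imaging.** Section 3.1.4.8 says that subjects who stop at maximum clinical benefit "must continue imaging every 12 weeks, and the investigator must ensure close monitoring of symptoms". The standard schedule is anchored to first dose: "Tumor imaging assessments will occur every 6 weeks from the date of first dose" for the first 24 weeks, then 12-weekly (Table 5.1-14a). Section 3.1.9.1 adds that, for subjects with disease control 3 years after first dose, the "tumor assessment schedule should be modified to every 24 weeks, unless clinically indicated, to continue tumor assessments every 12 weeks". Section 5.4 repeats this, timed at "3 years after the first dose or 3 years after re-initiation dose, as the case may be". The first column of Table 5.1-14b covers "All Subjects (Except Re-initiation Subjects"); its other column is for subjects who have already re-initiated. The only relief is the footnote: "Scans may continue every 12 weeks" if clinically indicated.

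**Earliest stop.** Section 3.1.4.1 requires "Minimum 24 months between first dose of study treatment and discontinuation for maximum clinical benefit" and, for responders, at least 12 months of treatment after first response.

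**Window.** The two bullets in Section 3.1.4.8 divide subjects by whether progression falls up to or beyond 52 weeks after last dose. Section 3.1.4.1 counts the 52 weeks once from discontinuation and once as weeks of follow-up. Section 3.1.9.1 starts follow-up at the decision to discontinue. Section 4.3.9 and the synopsis paragraph on re-initiation require progression within 1 year and name no starting date themselves, but Section 4.3.9 and other parts of the synopsis refer to Section 3.1.4.8. After its second bullet, Section 3.1.4.8 also bars re-initiation itself once 52 weeks have passed since discontinuation. Section 1.1.4.7 uses similar wording in its first paragraph, then states the progression-based rule later.

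The imaging row of Table 5.1-7 says "Refer to Figure 3.1.4.8-1" and also points to Table 5.1-14. That figure is not in the text available for this review.

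**The concern.** Re-treatment depends on progression being documented in time. If a site follows the follow-up tables to Table 5.1-14b, nothing there says that a subject inside the re-initiation window must stay on 12-weekly scans. A progression arising late in the window may then first be seen, and so dated, after the window has closed.

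The differing clock wordings raise a separate question. Two sites with the same patient could reach different answers, depending on whether they read Section 3.1.4.1, the bullets of Section 3.1.4.8, or the sentence that follows them.

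At stake are eligibility for individual patients near the end of the window and who enters the exploratory re-initiation analyses (ORR-R, PFS-R, OS-R and the others in Section 8.3.3).

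**Working it through.** The plan gives no figure to reproduce on this point. The check is calendar arithmetic on its rules.

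**1. Overlap with the 24-weekly period.** Inputs: earliest stop month 24 = week 104 (Section 3.1.4.1); window 52 weeks (Section 3.1.4.8); reduced schedule from 3 years = week 156 (Table 5.1-14b). For a stop at week W, overlap = min(52, max(0, W + 52 − 156)).

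- Month 24 (W = 104): 0 weeks
- Month 30 (W = 130): 26 weeks
- Month 36 (W = 156) or later: 52 weeks

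Later stops follow from the rules: a subject first responding at month 18 cannot stop before month 18 + 12 = 30.

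**2. Scheduled coverage lost.** On the nominal first-dose grid, 12-weekly scans fall on multiples of 12. Week 156 = 13 × 12 is on the grid, and 24-weekly scans then fall at 180, 204 and 228. Last scheduled scan inside the window (W to W + 52):

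| Stop week W | Window ends | 12-weekly | 24-weekly | Loss (weeks) |
|---|---|---|---|---|
| 104 | 156 | 156 | 156 | 0 |
| 116 | 168 | 168 | 156 | 12 |
| 128 | 180 | 180 | 180 | 0 |
| 140 | 192 | 192 | 180 | 12 |
| 152 | 204 | 204 | 204 | 0 |
| 164 | 216 | 216 | 204 | 12 |
| 176 | 228 | 228 | 228 | 0 |

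The loss alternates in 12-week bands: nil for stops in weeks 104 to <116, 128 to <140 and 152 to <164; 12 weeks (12/52 = 23%) for stops in weeks 116 to <128, 140 to <152 and 164 to <176.

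Sensitivity: suppose the whole window is after year 3 and the interval is counted instead from the restaging scan, s weeks before the stop. The last in-window scan at spacing d is floor((52 + s)/d) × d − s. At s = 0 this is 48 for both spacings. At s = 8 it is 52 for d = 12 and 40 for d = 24. The loss is again 0 or 12 weeks.

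**3. Window start.** Let g be the weeks from last dose to discontinuation. Progression at week t after last dose is eligible under the Section 3.1.4.8 bullets if t ≤ 52, and under Section 3.1.4.1 if t ≤ 52 + g. The protocol does not fix g. Assumed values:

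- g = 0: no disagreement
- g = 2 (stop decided at the next Q2W visit; C3, C5): weeks 53–54 disputed
- g = 4 (next Q4W visit; mStage, cStage): weeks 53–56 disputed
- g = 5: weeks 53–57 disputed

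A gap is foreseeable: the footnote to Table 5.1-7 provides for discontinuation more than 35 days (5 weeks) after last dose.

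**4. Closing event.** Let r be the weeks from progression to the first re-initiation dose, assumed to be 1 to 4. Table 5.1-8 allows the new baseline scan up to 28 days before that dose. The bullets allow a subject with t ≤ 52. The barring sentence excludes the same subject if t + r > 52 + g. With g = 0:

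- r = 1: progressions in week 52 are caught
- r = 4: progressions in weeks 49–52 are caught

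For example, progression at week 50 with a first dose at week 54 is allowed by the bullet and barred by the sentence. Because the sentence counts from discontinuation, the conflict needs r > g; with g = 4 and r ≤ 4 it vanishes.

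**The case against.** The best defence is that the protocol can be read coherently. Section 3.1.4.8 is specific and says *must*; the reduced schedule is general, says *should*, and allows 12-weekly scans when clinically indicated. Amendment 09 edited Section 3.1.4.8, and the current text keeps the 12-weekly requirement, which suggests intent. Unscheduled scans are collected (Section 5.3.1), and close symptom monitoring is required, so some progressions between scheduled scans would still be caught. On the clock, both Section 3.1.4.8 bullets count from last dose, and Section 4.3.9, the synopsis and Section 3.1.4.1 refer to that section. Progression is the qualifying event in the synopsis and in Sections 1.1.4.7, 3.1.4.1, 3.1.4.8 and 4.3.9. The barring sentence can be read as a loose restatement of the bullet before it.

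Most of this stands, and it rules out two stronger readings. A reader might infer that the imaging rules cannot both be obeyed; they can, by scanning 12-weekly. A reader might also infer that the window has no defined origin; the cross-references make last dose the operative one.

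What survives is narrower. The protocol states no order of precedence, the table to which sites are sent carries no exemption, and Section 3.1.4.1 and the barring sentence still say something different from the bullets. Figure 3.1.4.8-1 may settle either point for sites, but it would not remove the conflicting text.

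**Conclusion.** The point holds as a minor internal inconsistency. A site following only Table 5.1-14b would breach Section 3.1.4.8 for subjects who stopped later than month 24, once they pass year 3 inside the window. It would lose 0 or 12 weeks of scheduled coverage. The clock wordings disagree on progressions up to g weeks beyond week 52. The barring sentence catches progressions in at most the last 1 to 4 weeks of the window, and only when re-screening takes longer than g.

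These sizes rest on nominal scan dates (visit windows of 1 to 2 weeks blur the edges), scheduled scans only, and assumed values of g and r. The documents do not give the number of subjects affected.

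Two further inferences are not supported. One is that eligible patients will necessarily be denied re-treatment: the loss can be nil, and Section 4.3.6 separately allows case-by-case re-initiation at any time in consultation with the sponsor, although its reach to these subjects is arguable. The other is that the main efficacy result is compromised: the primary ORR and the Simon two-stage test do not depend on these rules.

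**What to change.** (a) In Table 5.1-14b and Sections 3.1.9.1 and 5.4, state that subjects who stopped at maximum clinical benefit stay on 12-weekly scans until 52 weeks after last dose, per Section 3.1.4.8.

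(b) Align Section 3.1.4.1, the barring sentence in Section 3.1.4.8 and the opening wording of Section 1.1.4.7 with the Section 3.1.4.8 bullets: re-initiation is not permitted if RECIST 1.1 progression occurs more than 52 weeks after last dose. Add that re-treatment should start promptly once re-screening is complete, so that the start is not left open-ended. Confirm that Figure 3.1.4.8-1 agrees.

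**Cost.** This is a short wording amendment needing IRB/IEC approval (Section 9.1.1). Affected subjects would have 0 to 3 more in-window scans than on the 24-weekly schedule, all already required by Section 3.1.4.8. On the nominal grid the maximum arises, for example, for a stop in weeks 164 to <168, which adds scans at 168, 192 and 216. The last-dose clock makes the window shorter by g than Section 3.1.4.1 implies (2 to 5 weeks for the non-zero gaps assumed above). Some subjects who progressed in time would start re-treatment after week 52, which the bullets already allow.
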